5.3 Dietary restrictions

On study visit days, all patients will fast (i.e. no food or liquid except water) for at least 6 hours prior to administration of study treatment and will continue to fast for at least 1 hour thereafter. No fluid intake apart from the fluid given at the time of drug intake is allowed from 1 h before until 1 h after dosing.

Alcohol consumption is to be strongly discouraged, and should not exceed 20 g/day in females and 30 g/day in males. Alcohol should be avoided for 8 hours prior to time of drug intake.

Patients can drink water *ad libitum* however, to ensure adequate hydration patients should have a fluid intake of at least 240 mL every 4 hours during waking hours in addition to fluid taken with meals and medication.

To keep the dietary intake as consistent as possible, patients participating in this study will be counseled regarding appropriate exercise and diet per local standards, e.g. instruction to carefully adhere to American Heart Association (AHA) diet or equivalent if there is a country specific recommended diet (see [Appendix 1](#)).

6 Treatment

6.1 Study treatment

Details on the requirements for storage and management of study treatment, and instructions to be followed for patient numbering, prescribing/dispensing and taking study treatment are outlined in the Site Operations Manual.

6.1.1 Investigational treatment and control drugs

The investigational drug, LMB763 and matching placebo, will be prepared by Novartis and supplied to the Investigator site as single blinded patient packs to be dispensed by the unblinded pharmacist at the investigator site. Study treatments are defined as:

- LMB763 capsules
- LMB763 capsules
- LMB763 capsules
- Matching placebo capsules

6.1.2 Additional study treatment

No additional treatment beyond investigational drug and control drug are included in this trial.

6.2 Treatment arms

Patients will be assigned to one of the following two treatments in a ratio of 2:1. Study treatments are defined as:

Cohort 1:

- LMB763 (1 × LMB763 capsule)
- Matching placebo (1 × Matching placebo capsule)

Cohort 2:

- LMB763 (2 × LMB763 capsules)
- Matching placebo (2 × Matching placebo capsules)

6.3 Treatment assignment and randomization

Randomized treatment will be assigned to individual patients by way of a randomization number. Randomization numbers will be assigned in ascending, sequential order to eligible patients (see Site Operations Manual for details).

The randomization number is only used to identify which treatment the patient has been randomized to receive. The Patient number assigned to a patient at screening remains the unique identifier for the patient throughout the study. For information on patient numbering, please see ‘Patient numbering’ section in the Site Operations Manual.

The randomization numbers will be generated using the following procedure to ensure that treatment assignment is unbiased and concealed from patients and investigator staff. A patient randomization list will be produced by the IRT provider using a validated system that automates the random assignment of treatment arms to randomization numbers. These randomization numbers are linked to the different treatment arms.

Randomization will be stratified by BMI at baseline (<30 kg/m² or ≥ 30 kg/m² for patients with an Asian race, or <35 kg/m² or ≥ 35 kg/m² for all other patients). The race will be based on the race the patient self-reports as captured on the demography eCRF.

The randomization scheme for patients will be reviewed and approved by a member of the Randomization Office.

Follow the details outlined in the Site Operations Manual regarding the process and timing of treatment assignment and randomization of patients.

Table 6-1 provides general details of the numbering of patients for randomization into each cohort:

Table 6-1 Treatment Assignment Numbering – Cohort 1

Corporate Confidential Information	Race	BMI (kg/ m ²)	Randomization Numbers
	Asian	<30	5101-5292
	Asian	≥30	5301-5492
	Non-Asian	<35	5501-5692
	Non-Asian	≥35	5701-5892

Table 6-2 Treatment Assignment Numbering – Cohort 2Corporate Confidential
Information

Race	BMI (kg/ m ²)	Randomization Numbers
Asian	<30	9101-9292
Asian	≥30	9301-9492
Non-Asian	<35	9501-9692
Non-Asian	≥35	9701-9892

6.4 Treatment blinding

This is a patient and investigator-blinded study. Patients and investigators will remain blinded to study treatment throughout the study, except where indicated below.

The identity of the treatments will be concealed by the use of study drugs that are all identical in packaging, labeling, schedule of administration, appearance, and odor.

Site staff

With the exception of any unblinded site staff identified below, all site staff (including study investigator and study nurse) will be blinded to study treatment (LMB763 or placebo) throughout the study.

Unblinding a single patient at site for safety reasons (necessary for patient management) will occur via an emergency system in place at the site (see [Section 6.7](#)).

Drug product will be supplied as single blinded patient packs, so an unblinded pharmacist (or appropriately trained site personnel) who is independent of the study team will be required in order to maintain the blind. This unblinded pharmacist will receive a randomization number and treatment allocation from the IRT system, and will then dispense the appropriate medications to the patient. Appropriate measures must be taken by the unblinded pharmacist to ensure that the treatment assignments are concealed from the rest of the site staff.

Note that the IRT system will not be used for any drug accountability or dispensing procedures. IRT is only used for enrollment tracking in this study.

Sponsor staff

The sponsor will remain unblinded to the treatment assignment of all patients to allow for continuous unblinded safety monitoring throughout the study.

The unblinded field monitors are required to review drug accountability and allocation at site. The unblinded monitors will be unblinded through review of source documentation compiled by the unblinded pharmacist, which details treatment allocation to individual patients. The unblinded monitors will also be able to review the treatment allocation provided to the unblinded pharmacist via the IRT system.

The clinical trial team is allowed to share unblinded results with other sponsor staff (e.g. decision boards) as required for internal decision making on the study or the project while the study is ongoing.

6.5 Treating the patient

Study medication will be self-administered by the patient orally once daily (refer to [Section 3.1](#) for 12 weeks (84 days). On visit days, treatment will be administered at the site. All study treatment will be administered under fasted conditions (no food or drink for at least 6 hours). On Day 1 (V3) and Day 42 (V7), a meal will be provided at least 4 hours post-dose. See the Site Operations Manual for further details.

Sponsor qualified medical personnel will be readily available to advise on trial related medical questions or problems.

6.6 Permitted dose adjustments and interruptions of study treatment

Safety and tolerability

In the event of a significant safety/tolerability concern which does not meet study stopping criteria ([Section 7.5](#)), and is not related to ALT and/or AST elevations, temporary interruption and dose adjustments are permitted as follows in order to allow the patient to continue on study treatment:

- Cohort 1: Reduction in dose frequency to every alternate day
- Cohort 2: Reduction in dose

Investigators must use their medical judgment in regards to what they deem as the best interest of the patient.

Significant isolated ALT and/or AST increase

In the event of a significant ALT and/or AST elevation, temporary interruption and dose reduction is permitted in order to allow the patient to continue on study treatment. The guidance for the modification of study treatment is outlined below and in [Table 6-3](#); this will allow an evaluation of whether such dose reductions are useful in patient management. The ability to reduce the dose is clinically relevant as data generated after dose reduction will provide further information regarding the tolerability and safety of LMB763.

If the patient has symptoms or other LFT abnormalities, in particular elevations of bilirubin and/or PT/INR and/or ALP), refer to [Section 9.3](#) and [Table 9-2](#) for appropriate actions.

Triggers related to ALT and/or AST elevation are described in [Table 9-1](#). A significant ALT and/or AST increase is defined as (i) in the presence of symptoms or other liver function abnormalities $> 3 \times \text{ULN}$, **AND in the case of elevated baseline $> 2 \times \text{Baseline value}$** ; (ii) in the absence of symptoms or other liver function abnormalities ALT and/or AST elevation $> 5 \times \text{ULN}$ **AND in the case of elevated baseline $> 2 \times \text{Baseline value}$** . All cases with ALT and/or AST elevation $> 3 \times \text{ULN}$ will be captured as a liver event per [Table 9-1](#) and instructions for further assessment detailed in [Table 9-2](#). Patients who experience significant isolated ALT and/or AST elevations will be instructed to return to the clinic within 48-72 hours for an additional laboratory evaluation to confirm these results, as defined in [Table 6-3](#). The laboratory tests to be repeated are ALT, AST, GGT, alkaline phosphatase, total bilirubin, and albumin (LFT) and PT/INR.

The guidance for the modification of study treatment is outlined below in [Table 6-3](#).

If the additional laboratory evaluation confirms a significant increase of ALT and/or AST values, the dose frequency will be reduced to every alternate day (cohort 1), or the dose will be reduced (cohort 2); the investigator and site personnel will remain blinded to the identity of treatment. The investigator must document the patient's dose frequency reduction in source documents.

If the additional laboratory evaluation does not confirm the significant increase of ALT or AST values, the patient will continue with the assigned/original treatment.

If the additional laboratory evaluation shows a higher elevation of ALT and/or AST (e.g. > 8 x ULN) as compared to the original elevation (e.g. > 5 x ULN but < 8 x ULN), the guidance for this higher elevation (e.g. > 8 x ULN) should be followed.

Actions should be based on whichever of AST and ALT has a higher multiple of ULN or baseline value. In order to allow for variation in laboratory results, persisting elevation is defined as the value remaining at $\geq 90\%$ of the original elevated value. When there is a marked difference in multiple of ULN between ALT and AST, medical judgment should be applied to distinguish between persisting and decreasing. If at any time the repeat testing shows levels in a higher category, the guidance for the higher category should be followed.

Only one cycle of dose frequency/dose reduction is allowed. If, despite being on a reduced dose, a patient has persistent or new significant ALT and/or AST elevations, the patient must be discontinued from study treatment (refer to [Section 7.2](#)). After discontinuation for a liver-related event, LFT and clinical monitoring should continue until the event is resolved (refer to [Section 9.3](#)). Increasing the dose to the original level is not permitted.

Table 6-3 Dosing response to Isolated ALT/AST Elevations

ALT and/or AST increase	First Action	Result	2nd Action	Result	3rd Action
> 2 x baseline AND ≤5 x ULN	Repeat tests ¹ within 48-72 hours	Elevation ² of ALT and/or AST confirmed	Initiate close observation of patient. Repeat tests ¹ within 48 – 72 hours	Persistent elevation ² of ALT and/or AST for 1 week	Cohort 1: Reduce Dose frequency to alternate day dosing Cohort 2: Reduce LMB763 dose Continue close observation of patient with minimum twice weekly testing ¹ (once weekly if stable) until ALT and AST <3x ULN (or 2x baseline if elevated before drug exposure). If ALT and AST levels remain ≥3x ULN three weeks after dose reduction, discontinue study treatment
		Decreasing ALT and AST ³		Continue assigned study treatment as per protocol	
		Decreasing ALT and AST ³	Continue assigned study treatment as per protocol	--	--
> 2 x baseline AND >5 x ULN but ≤ 8 x ULN	Repeat tests ¹ in 48 hours	Elevation ² of ALT and/or AST confirmed	Cohort 1: Reduce Dose frequency to alternate day dosing Cohort 2: Reduce LMB763 dose Initiate close observation of patient. Repeat tests ¹ within 48 – 72 hours	Persistent elevation ² of ALT and/or AST	Discontinue study treatment
		Decreasing ALT and AST ³		Continue with reduced dose frequency or reduced dose Continue close observation of patient with minimum twice weekly testing ¹ (once weekly if stable) until ALT and AST < 3 x ULN and < 2 x baseline. If ALT and AST levels remain ≥3 x ULN three weeks after dose reduction, discontinue study treatment	
		Decreasing ALT and AST ³	Continue assigned study treatment as per protocol	--	--
>2 x baseline AND >8 x ULN	Discontinue study treatment	--	--	--	--

¹Tests: A physical examination should be performed and recorded in source documents. PT/INR, ALT, AST, GGT, alkaline phosphatase, total bilirubin, and albumin; these repeats must be performed using the central laboratory if possible and captured via the unscheduled lab CRF. If this is not possible, then the repeats can be performed at a local laboratory to monitor the safety of the patient. If tests are performed at local laboratory, results will be captured in source documents only.

²Persistent: either ALT and/or AST remain > 90% of the original elevated level

³Decreasing: both ALT and AST levels decrease to ≤ 90 % of the original elevated level. Medical judgement should be applied if there is a marked difference between ALT and AST multiples

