All follow-up information, and the procedures performed must be recorded as appropriate in the CRF.

Table 9-2 Actions required for Liver Events

Criteria	Actions required	Follow-up monitoring
Potential Hy's Law case ^a	
 • Discontinue the study drug immediately • Hospitalize, if clinically appropriate • Establish causality 	ALT, AST, TBL, Alb, PT/INR, ALP and GGT until resolution ^c (frequency at investigator discretion)
ALT or AST		
$> 8 \times$ ULN and $> 2 \times$ baseline value	
 • Discontinue the study drug immediately • Hospitalize if clinically appropriate • Establish causality 	ALT, AST, TBL, Alb, PT/INR, ALP and GGT until resolution ^c (frequency at investigator discretion)
$> 3 \times$ ULN and $> 2 \times$ baseline value and INR > 1.5	
 • Discontinue the study drug immediately • Hospitalize, if clinically appropriate • Establish causality 	ALT, AST, TBL, Alb, PT/INR, ALP and GGT until resolution ^c (frequency at investigator discretion)
$> 5 \times$ ULN and $> 2 \times$ baseline value but $\leq 8 \times$ ULN	
 • Repeat LFT within 48 hours • If elevation is confirmed, refer to Table 6-3 	Refer to Table 6-3 ALT, AST, TBL, Alb, PT/INR, ALP and GGT until resolution ^c (frequency at investigator discretion)
$> 3 \times$ ULN and $> 2 \times$ baseline value, accompanied by symptoms ^b	
 • Discontinue the study drug immediately • Hospitalize if clinically appropriate • Establish causality 	Refer to Table 6-3 ALT, AST, TBL, Alb, PT/INR, ALP and GGT until resolution ^c (frequency at investigator discretion)

Criteria	Actions required	Follow-up monitoring
> 3 to ≤ 5 × ULN if normal baseline or >2 × baseline if elevated before drug exposure (patient is asymptomatic)	
 Repeat LFT within 48-72 hours If elevation is confirmed, refer to Table 6-3 	
Refer to Table 6-3
 
Investigator discretion

ALP (isolated)		
> 2 × ULN if normal baseline (in the absence of known bone pathology)	
 Repeat LFT within 48 hours If elevation persists, establish causality Complete liver CRF 	
Investigator discretion
 
Monitor LFT within 1 to 4 weeks or at next visit

TBL (isolated)		

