> 2 × ULN if normal baseline (in the absence of known Gilbert syndrome)	
 Repeat LFT within 48 hours If elevation persists, discontinue the study drug immediately Hospitalize if clinically appropriate Establish causality Complete liver CRF 	
ALT, AST, TBL, Alb, PT/INR, ALP and GGT until resolution^c (frequency at investigator discretion)
 
Test for hemolysis (e.g., reticulocytes, haptoglobin, unconjugated [indirect] bilirubin)

> 1.5 to ≤ 2 × ULN (patient is asymptomatic)	
 Repeat LFT within the next week If elevation from baseline is confirmed, initiate close observation of the patient 	
Investigator discretion
 
Monitor LFT within 1 to 4 weeks or at next visit

Jaundice	
 Discontinue the study drug immediately Hospitalize the patient Establish causality Complete liver CRF 	
ALT, AST, TBL, Alb, PT/INR, ALP and GGT until resolution^c (frequency at investigator discretion)

Any AE potentially indicative of a liver toxicity*	
 Consider study drug interruption or discontinuation Hospitalization if clinically appropriate Establish causality Complete liver CRF 	
Investigator discretion

*These events cover the following: hepatic failure, fibrosis and cirrhosis, and other liver damage-related conditions; the non-infectious hepatitis; the benign, malignant and unspecified liver neoplasms

^aElevated ALT/AST > 3 × ULN and TBL > 2 × ULN but without notable increase in ALP to > 2 × ULN

^b(General) malaise, fatigue, abdominal pain, nausea, or vomiting, or rash with eosinophilia

^cResolution is defined as an outcome of one of the following: (1) return to baseline values, (2) stable values at three subsequent monitoring visits at least 2 weeks apart, (3) remain at elevated level after a maximum of 6 months, (4) liver transplantation, and (5) death.

Table 9-3 Exclusion of underlying liver disease

Disease	Assessment
Hepatitis A, B, C, E	
 IgM anti-HAV; HBSAg, IgM anti-HBc, HBV DNA; anti-HCV, HCV RNA, IgM & IgG anti-HEV, HEV RNA
CMV, HSV, EBV infection	
 IgM & IgG anti-CMV, IgM & IgG anti-HSV; IgM & IgG anti-EBV
Autoimmune hepatitis	
 ANA & ASMA titers, total IgM, IgG, IgE, IgA
Alcoholic hepatitis	
 Ethanol history, gGT, MCV, CD-transferrin

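### Table 9-2 has no mandatory stop for ALT/AST > 3 × ULN with bilirubin > 2 × ULN once ALP has risen above 2 × ULN, unless another stop criterion is met

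*Protocol*

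**What the plan says.** All references are to the protocol; the SAP does not address patient-level stopping.

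- **Section 6.6** gives dosing rules for raised ALT/AST. For combined abnormalities ("If the patient has symptoms or other LFT abnormalities, in particular elevations of bilirubin and/or PT/INR and/or ALP") it sends the site to Section 9.3 and Table 9-2.
- **Table 9-2, potential Hy's Law row**, requires an immediate stop. Footnote a defines the case as ALT/AST > 3 × ULN and TBL > 2 × ULN "but without notable increase in ALP to" > 2 × ULN. Table 9-1 carries the same ALP limit.
- **Table 9-2, TBL block**, is headed as applying to isolated elevations. For TBL > 2 × ULN from a normal baseline it says: "If elevation persists, discontinue the study drug immediately".
- **Table 9-2, ALP block**, is also headed as isolated. It asks for a repeat test, a causality assessment and a CRF page, and does not stop dosing.
- **Table 9-2, ALT/AST rows below 8 × ULN** (no symptoms, INR ≤ 1.5) ask for a repeat test and then: "If elevation is confirmed, refer to Table 6-3".
- **Table 6-3** is titled "Dosing response to Isolated ALT/AST Elevations". Its steps depend on ALT and AST alone.
- **Other stop rows in Table 9-2** need ALT/AST > 8 × ULN and > 2 × baseline; or > 3 × ULN and > 2 × baseline with INR > 1.5 or with symptoms; or clinical jaundice.

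**The concern.** A mandatory stop should not weaken as the liver picture gets worse. Here it does. Take a patient with ALT/AST > 3 × ULN and TBL > 2 × ULN. If ALP is at or below 2 × ULN, the drug stops at once. If ALP has risen above 2 × ULN, so that three tests are abnormal instead of two, no row requires a stop on that combination. Bilirubin raised on its own is treated more strictly, because it requires a stop if it persists.

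The ALP condition makes sense as part of a Hy's Law label, where it separates hepatocellular from cholestatic injury. It is a weak switch for a stop rule in this trial. Section 3.3 calls ALP an FXR responsive marker and reports that it rose without a rise in GGT or 5'NT. A drug-related ALP rise could therefore take a patient out of the one rule that protects against combined ALT and bilirubin elevation. At stake is the safety of individual patients in a first-in-patient study whose primary objectives include safety. No power, sample size or efficacy figure is affected.

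**Working it through.** No figure in the plan is being challenged. The check applies each row of Table 9-2 to defined patients. ALT/AST, TBL and ALP are in multiples of ULN. Except in the last row of the table below, the patient has no symptoms or jaundice, INR is normal, and a raised ALP is one that has increased on study.

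| ALT/AST | Relative to baseline | TBL | ALP | Row that applies | Mandatory action |
|---|---|---|---|---|---|
| 4 | > 2 × | 2.5 | 1 | Hy's Law | Immediate stop |
| 4 | > 2 × | 2.5 | 2.5 | > 3 to ≤ 5 × ULN | Repeat, then Table 6-3 |
| 6 | > 2 × | 2.5 | 1 | Hy's Law | Immediate stop |
| 6 | > 2 × | 2.5 | 2.5 | > 5 to ≤ 8 × ULN | Repeat, then Table 6-3 |
| 9 | > 2 × | 2.5 | 2.5 | > 8 × ULN | Immediate stop |
| 4, 6 or 9 | ≤ 2 × | 2.5 | 1 | Hy's Law | Immediate stop |
| 4, 6 or 9 | ≤ 2 × | 2.5 | 2.5 | No ALT/AST or TBL row | No mandatory stop |
| 1 | – | 2.5 | 1 | TBL (isolated) | Stop if it persists |
| 4 | > 2 × | 2.5 | 2.5, plus INR 1.6, symptoms or jaundice | INR, symptom or jaundice row | Immediate stop |

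**What Table 6-3 then does.** For the patient at ALT 4 × ULN, its first row repeats the tests in 48–72 hours. A decrease means that ALT and AST have both fallen to ≤ 90% of the first value; for ALT, 0.9 × 4 = 3.6 × ULN. If ALT is then 3.5 × ULN (3.5 / 4 = 87.5%) and AST has fallen likewise, the assigned treatment continues, even if TBL is still 2.5 × ULN. If the rise is confirmed, the row leads to observation, a dose reduction after a week of persistence, and a stop if ALT/AST are still ≥ 3 × ULN three weeks after reduction. For the patient at 6 × ULN, a confirmed rise leads to a dose reduction, with a stop if ALT/AST persist at the next repeat. If ALT and AST have fallen to ≤ 90% (for ALT, 0.9 × 6 = 5.4 × ULN), the assigned treatment again continues. TBL and ALP are in the repeat panel, but no step acts on them.

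**The ≤ 2 × baseline case.** Exclusion criterion 18 admits ALT/AST up to 5 × ULN. With a baseline of 4.5 × ULN, a value of 9 × ULN is 9 / 4.5 = 2.0 × baseline. That is not above 2, so the > 8 × ULN row does not apply. The Hy's Law row has no baseline-multiple condition and would stop this patient if ALP were ≤ 2 × ULN.

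**What else could require a stop.** The liver item in Section 7.2 points back to Section 9.3 and Tables 9-1 and 9-2. Its item on related Grade 3 events excludes liver events. The remaining routes rest on opinion: abnormal values that the investigator judges a safety risk (Section 7.2), consideration of interruption (Section 9.3), and the Table 9-2 row for adverse events suggesting liver toxicity, which asks the site to consider interruption or discontinuation.

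**The case against.** The strongest objection is that the argument gives weight to the word isolated in the TBL heading but not in the title of Table 6-3. Read consistently, there are two outcomes. If the headings bind, Table 6-3 does not govern this patient, and the general follow-up in Section 9.3 applies: repeat tests, close observation and possible interruption. If they do not bind, the TBL row stops the drug when the rise persists. Both readings are fair, and the cross-reference "If elevation is confirmed, refer to Table 6-3" makes a third, mixed reading possible. None of the three restores the immediate stop. The first leaves only discretion, and the second waits for persistence. What stands of the objection is that no particular number of days of continued dosing can be claimed.

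The sponsor is also unblinded and monitors safety continuously, and Section 3.2 names ALT specifically. That lowers the risk, but it is not a patient-level rule, and Section 10.4 requires no data monitoring committee.

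Three stronger readings are tempting and are not supported.

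- *The Section 6.6 text contradicts Table 6-3 at > 3 to ≤ 5 × ULN.* The definition "A significant ALT and/or AST increase is defined as (i) in the presence of symptoms or other liver function abnormalities" starts at > 3 × ULN. It could be combined with "If the additional laboratory evaluation confirms a significant increase of ALT and/or AST values, the dose frequency will be reduced" and the later rule that when "a patient has persistent or new significant ALT and/or AST elevations, the patient must be discontinued from study treatment", giving faster action than Table 6-3. But those action sentences stand under a sub-heading for isolated increases and refer back to isolated elevations. The examples there are > 5 and > 8 × ULN, and patients with other abnormal liver tests are sent to Table 9-2. Context largely resolves the point.
- *Entry with ALP at 2–3 × ULN disables the Hy's Law row from the start.* Criterion 18 allows such entry, but the footnote speaks of a notable increase. A patient whose ALP has not risen can still fall in that row.
- *The protocol orders continued dosing.* It does not. The investigator may always stop; what is missing is the requirement.

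**Conclusion.** The gap is real and narrow. It concerns patients without symptoms or jaundice, with INR ≤ 1.5, ALT/AST > 3 × ULN (up to 8 × ULN, or higher if ≤ 2 × baseline), TBL > 2 × ULN, and ALP that has risen above 2 × ULN. For them no Table 9-2 row requires a stop on the combination, whereas the same ALT and TBL with ALP ≤ 2 × ULN require one immediately. Outside those limits the other stop rows apply whatever the ALP.

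The conclusion rests on taking footnote a and the isolated heading of the TBL block as written. If a site ignored that heading, the rule would still be weaker: a stop on persistence instead of an immediate one. The documents give no size or frequency for ALP rises, and Section 3.3 is partly redacted, so the number of patients affected is unknown. The point should be corrected because it is a patient-safety rule, ALP is expected to respond to the drug, and the correction is small.

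**What to change.** Add one row to Table 9-2: *ALT or AST > 3 × ULN with TBL > 2 × ULN, whatever the ALP: immediate discontinuation of study drug*. Give it the same further actions and follow-up monitoring as the potential Hy's Law row.

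- Do not attach a > 2 × baseline condition. The Hy's Law row has none, and because entry allows ALT up to 5 × ULN, the condition would leave part of the gap open.
- Leave the Hy's Law definition unchanged, so that event labelling and reporting stay the same.

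The cost is one table row in a protocol amendment. No tests are added, because ALT, AST, ALP, TBL and INR are already in the repeat panel. The downside is that a few patients with all three tests raised, possibly including some whose ALP rise is only a drug effect, would stop earlier than they might under investigator discretion.

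### Section 6.6 and Table 9-2 do not give one clear action for a symptomatic ALT/AST rise above 3 and up to 8 × ULN

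*Protocol*

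**What the plan says.** Protocol Section 6.6, under a subheading about significant isolated ALT/AST increases, does four things.

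- It opens with a permission: "In the event of a significant ALT and/or AST elevation, temporary interruption and dose reduction is permitted".
- It redirects some patients: "If the patient has symptoms or other LFT abnormalities, in particular elevations of bilirubin and/or PT/INR and/or ALP), refer to" Section 9.3 and Table 9-2.
- It defines the key term with two limbs. Limb (i): "A significant ALT and/or AST increase is defined as (i) in the presence of symptoms or other liver function abnormalities", with a threshold of more than 3 × ULN and, where baseline is elevated, more than 2 × baseline. Limb (ii) covers patients without symptoms or other abnormalities and uses more than 5 × ULN, with the same baseline condition.
- It sets the response. The repeat test is for isolated rises: "Patients who experience significant isolated ALT and/or AST elevations will be instructed to return to the clinic within 48-72 hours". The next step is worded without that limit: "If the additional laboratory evaluation confirms a significant increase of ALT and/or AST values, the dose frequency will be reduced to every alternate day" in Cohort 1, with a lower dose in Cohort 2. If the rise is not confirmed, the patient stays on the assigned treatment.

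Table 6-3, whose title restricts it to isolated elevations, gives the detailed steps.

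Table 9-2 in Section 9.3 has a row for ALT or AST above 3 × ULN and above 2 × "baseline value, accompanied by symptoms". Its action is "Discontinue the study drug immediately". Its follow-up column nevertheless refers to Table 6-3. A separate row, for above 5 and up to 8 × ULN and above 2 × baseline, calls for a retest within 48 hours and then Table 6-3. That row does not mention symptoms. The row for above 3 and up to 5 × ULN is marked as asymptomatic.

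**The concern.** A defined term that includes symptomatic rises is used, without qualification, as the trigger for dose reduction. The table to which symptomatic patients are redirected stops treatment at the same threshold, but also points back to the dose-reduction table. Part of its range is covered by a second row with a different action.

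The stake is mainly patient safety. In a multicentre trial with blinded investigators, two sites could read the text differently: one stops drug at once, the other keeps a symptomatic patient on drug while a repeat is awaited. A secondary stake is the data. ALT change at Week 12 is the primary efficacy variable, and SAP Sections 6.1.3 and 7.2 plan analyses and tables of dose adjustments. Whether such a patient is recorded as dose-adjusted or as discontinued would then depend on the site's reading.

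**Working it through.** The plan states no figure on this point, so the check compares thresholds and actions.

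**1. Do the two texts select the same patient?** Let *b* be baseline and *x* the on-treatment value, both as multiples of ULN, in a patient with symptoms.

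- Section 6.6 limb (i): *x* > 3 and, if *b* > 1, *x* > 2*b*.
- Table 9-2 symptomatic row: *x* > 3 and *x* > 2*b*.

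If *b* ≤ 1, then 2*b* ≤ 2, so *x* > 3 already implies *x* > 2*b*. If *b* > 1, the conditions are identical. Both reduce to *x* > max(3, 2*b*), so they select the same symptomatic patients. This assumes that symptoms in Section 6.6 means those in the Table 9-2 footnote; Section 6.6 gives no list of its own.

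**2. What does each text say for that patient?**

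| Place | Scope as worded | Action |
|---|---|---|
| 6.6, redirect sentence | symptoms or other LFT abnormalities | go to Section 9.3 and Table 9-2 |
| 6.6, opening permission | significant (limb (i) included) | interruption and dose reduction permitted |
| 6.6, repeat test | significant and isolated | return in 48-72 hours |
| 6.6, after the repeat | significant; isolated not repeated | reduce if confirmed, original treatment if not |
| Table 9-2, symptomatic row, actions | > 3 × ULN, > 2 × baseline, symptoms | immediate discontinuation |
| Table 9-2, symptomatic row, follow-up | same | Table 6-3, plus liver tests until resolution |
| Table 9-2, > 5 to ≤ 8 × ULN row | > 2 × baseline; silent on symptoms | retest within 48 hours, then Table 6-3 if confirmed |

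**3. Overlap inside Table 9-2.** Take a symptomatic patient with *b* = 1 and *x* = 6. The symptomatic row is met, since 6 > 3 and 6 > 2. The > 5 to ≤ 8 row is also met, since 5 < 6 ≤ 8 and 6 > 2. One row stops treatment; the other retests and, through Table 6-3, reduces the dose or its frequency if the rise is confirmed. Section 6.6 tells sites to follow the higher category when repeat values rise, but that rule concerns enzyme level and does not rank a symptomatic row against a level-only row.

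**4. Range affected.** The upper end is 8 × ULN, because above that (with > 2 × baseline) Tables 6-3 and 9-2 both discontinue.

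| Baseline *b* | Symptomatic range in question, max(3, 2*b*) to 8 | Two-row overlap, max(5, 2*b*) to 8 |
|---|---|---|
| ≤ 1.5 | > 3 to 8 | > 5 to 8 |
| 2 | > 4 to 8 | > 5 to 8 |
| 3 | > 6 to 8 | > 6 to 8 |
| ≥ 4 | none | none |

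Exclusion criterion 18 admits ALT and AST up to 5 × ULN, so every line of this table can occur.

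**5. Other liver function abnormalities.** Limb (i) also covers these, but Table 9-2 treats them separately. Among ALT/AST rises, potential Hy's Law cases and INR above 1.5 stop treatment at once, and so does jaundice; isolated ALP does not. The conflict shown here is therefore limited to the symptomatic part of limb (i).

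**The case against.** The strongest reply is that Section 6.6 already decides the matter. Its one sentence directed at symptomatic patients sends them to Table 9-2, whose action column is plain. Limb (i) is only a definition. The repeat test is for isolated rises, and the dose-reduction sentence follows on from that test, so a redirected patient never reaches it. Section 7.2 also sends liver-related discontinuation to Section 9.3 and its tables. Limb (i) has another sensible use: a patient already on a reduced dose who has a persistent or new significant rise must stop. The Table 6-3 reference sits in a monitoring column, and Table 6-3 does contain monitoring steps. Section 9.3 asks for a 48-72 hour repeat after every liver event, so a repeat does not by itself mean staying on drug.

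Most of this stands. A reader might infer that Section 6.6 plainly orders a repeat test and dose reduction for symptomatic patients; the redirect and the isolated wording do not support that. Nor would Table 6-3, even if misapplied at up to 5 × ULN, reduce the dose after one confirmatory test: it requires the elevation to persist for 1 week. A reader might also infer that every symptomatic patient receives conflicting instructions. That too goes beyond the text, because a careful reader can reach discontinuation by following the redirect.

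What the reply does not answer lies at the redirect's destination. The symptomatic row refers to a table written for isolated rises, and the > 5 to ≤ 8 × ULN row also captures symptomatic patients. Section 7.2 points to Table 9-2 without saying which of its rows prevails.

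**Conclusion.** The point holds as an inconsistency of wording with a safety consequence, and it should be corrected. It is not a finding that the protocol directs symptomatic patients to remain on drug.

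It concerns symptomatic patients with ALT or AST above 3 and up to 8 × ULN and above twice baseline. It is strongest above 5 and up to 8 × ULN, where two rows of Table 9-2 apply with different actions. From above 3 to 5 × ULN it is weaker: Table 9-2's action is single there, and the doubt comes from the unqualified wording of Section 6.6 and the Table 6-3 cross-reference. It does not arise above 8 × ULN and does not extend to all other liver function abnormalities.

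The documents give no rate of such events and no data on how sites read the text, so neither the number of patients nor the effect on the ALT analysis can be stated. The conclusion assumes that the rows of Table 9-2, in particular the follow-up cell of the symptomatic row, are laid out in the source document as they appear in the extracted text.

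**What to change.** Reconcile four items so that a symptomatic elevation leads to one stated action, or so that the text says which instruction takes precedence:

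1. limb (i) of the definition in Section 6.6;
2. the permission and dose-reduction sentences in Section 6.6 that use the defined term without the word isolated;
3. the symptomatic row of Table 9-2, including its reference to Table 6-3;
4. the > 5 to ≤ 8 × ULN row of Table 9-2, which should say whether it applies to symptomatic patients.

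Which action applies is for the sponsor's clinicians; this review takes no position. The cost is wording in one section and one table, through an amendment with the approvals in Section 13.1 and notice to sites. No change to visits, sample size or the planned analyses is needed.
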